This statistical analysis plan (SAP) describes the planned analysis and reporting for Teva Branded Pharmaceutical Products R&D, Inc. study TV7820-IMG-10082 (A Phase I, Open-Label, Single-Dose, Adaptive (S)-(-)-[¹⁸F]fluspidine and [¹⁸F]fallypride Positron Emission Tomography Study to Evaluate Sigma-1 and Dopamine-2 Receptor Occupancy by Pridopidine in the Human Brain of Healthy Volunteers and in Patients with Huntington's Disease).

The following documents are used or referred to for the SAP generation:

- Clinical study protocol with Amendment 01, Approval date 11 November 2016
- Case report forms (CRFs) for Study TV7820-IMG-10082
- International Council for Harmonisation (ICH) E9 Guidance on Statistical Principles for Clinical Trials
- ICH E3 Structure and Content of clinical study reports

The reader of this SAP is encouraged to read the study protocol for details on the conduct of this study, the operational aspects of clinical assessments, and the timing for completing the participation of a subject in this study.

The SAP is intended to be in agreement with the protocol, especially with regards to the primary and all secondary endpoints and their respective analyses. However, the SAP may contain more details regarding these particular points of interest, or other types of analyses (eg, other endpoints). When differences exist in descriptions or explanations provided in the study protocol and this SAP, the SAP prevails; the differences will be explained in the clinical study report (CSR).

1. STUDY OBJECTIVES AND ENDPOINTS

1.1. Primary and Secondary Study Objectives and Endpoints

1.1.1. Primary and Secondary Study Objectives

The primary objective of this study are:

- To demonstrate target engagement, receptor binding/occupancy (RO) of pridopidine to sigma-1 receptors (S1R) in the brain (whole brain, cortical and subcortical regions) of healthy subjects and (optional) Huntington's disease (HD) patients after single oral dose administration;
- To establish the relationship between the plasma pridopidine concentrations and the S1R occupancy in the brain of healthy subjects and (optional) HD patients following a single oral dose of pridopidine.

The secondary objectives of this study are:

- To establish test-retest variability of (S)-(-)-[¹⁸F]fluspidine positron emission tomography (PET) imaging of S1R in healthy subjects;
- To evaluate the pharmacokinetics of pridopidine following single oral administration in healthy subjects and (optional) HD patients;
- To assess safety of pridopidine in healthy subjects and (optional) HD patients.

1.1.2. Endpoints

1.1.2.1. Pharmacodynamic Endpoints

The PET acquisition, as well as advanced magnetic resonance imaging (MRI) protocols (MRI-based Attenuation Correction [MR-AC], T1-weighted rapid 3-dimensional gradient-echo technique [T1 MPRAGE 3D], arterial spin labeling [ASL], 2D multi-voxel magnetic resonance spectroscopy [MRS], and resting state functional magnetic resonance imaging [rs-fMRI]) will be detailed in dedicated imaging manuals. These will also contain an analysis plan explaining how the imaging data is calculated. Imaging manuals will be provided prior to initiating the study.

1.1.2.2. Pharmacokinetic Endpoints

Blood samples for analysis of pridopidine and the metabolite TV-45065 will be obtained up to 24 hours after dosing. Pharmacokinetic parameters to be calculated are detailed in Section 9.2.

1.1.2.3. Safety and Tolerability Endpoints

The safety and tolerability endpoints are:

- occurrence of adverse events during the study
- clinical laboratory (serum chemistry, hematology, and urinalysis) test results

- vital signs (blood pressure [BP], respiratory rate, body temperature, and pulse) measurements at each visit
- electrocardiogram (ECG) findings
- physical examination findings, including body weight measurements
- use of concomitant medication during the study
- number (%) of subjects who did not complete the study (end of study)
- number (%) of subjects who did not complete the study due to adverse events

1.1.2.4. Biomarker Endpoints

1.1.2.5. Pharmacogenetic Endpoints

1.2. Exploratory Objectives and Endpoints

1.2.1. Exploratory Objectives

Exploratory objectives are:

- To explore a potential impact of endogenous corticoid levels on RO of pridopidine to S1R;
- To explore target engagement, RO of pridopidine to the dopamine-2 receptors (D2R) in the brain of healthy subjects and (optional) HD patients;
- To explore the relationship between the plasma pridopidine concentrations and D2R occupancy in the brain of healthy subjects and (optional) HD patients following a single oral dose of pridopidine;
- To establish the relationship between the plasma metabolite TV-45065 concentrations and the S1R occupancy in the brain following a single oral dose of pridopidine to healthy subjects and (optional) HD patients;
- To evaluate the relationship between plasma pridopidine concentration and brain activity using functional magnetic resonance imaging (MRI-based Attenuation Correction [MR-AC], T1-weighted rapid 3-dimensional gradient-echo technique [T1 MPRAGE 3D], Arterial Spin Labeling [ASL], 2D multi-voxel Magnetic Resonance Spectroscopy [MRS], and resting state functional Magnetic Resonance Imaging [rs-fMRI]);
- To evaluate the relationship between S1R and D2 receptor occupancy in vivo by pridopidine and brain activity using functional magnetic resonance imaging (MR-AC, T1 MPRAGE 3D, ASL, 2D MRS, and rs-fMRI);

- To explore any effects of pridopidine on brain activity, and link it to the occupancy of S1R and D2R;
- [REDACTED]
- [REDACTED]
- [REDACTED]

1.2.2. Exploratory Endpoints

Exploratory endpoints will be defined in the imaging analysis plan.

2. STUDY DESIGN

2.1. General Design

This is a Phase 1, single-dose, open-label, adaptive design (S)-(-)-[¹⁸F]fluspidine PET study in healthy subjects and (optional) in patients with HD designed to demonstrate target engagement and to assess the occupancy of the S1R by pridopidine. PET with the tracer (S)-(-)-[¹⁸F]fluspidine will be used to quantify changes in S1R availability following the administration of pridopidine (Part A). Binding of pridopidine to D2R may be assessed using PET imaging with [¹⁸F]fallypride (Part B, optional).

Since endogenous corticoid hormones have been described to competitively bind to S1R, the test-retest variability of (S)-(-)-[¹⁸F]fluspidine PET will be determined in 3 healthy subjects up-front or in parallel (Part 0). To minimize variability associated with the potential impact of circadian corticoid plasma level changes, individual scan and re-scan sessions will be performed at comparable times of the day for all subjects.

In addition, plasma corticoid levels (to include dehydroepiandrosterone [DHEA], progesterone, testosterone, cortisol, and, where feasible, androstanolone, allopregnanolone, pregnenolone) will be assessed immediately before each (S)-(-)-[¹⁸F]fluspidine or [¹⁸F]fallypride injection in all subjects.

Pharmacogenetic samples will be collected at screening for cytochrome P450 2D6 (CYP2D6) and exploratory genotyping. Biomarker pharmacodynamic samples will be collected at visit 3, prior to dosing and 4, 8, and 24 hours post pridopidine dose (a 10-minute window will be allowed).

The PET imaging will consist of subsets of PET scans that will be acquired in list mode: 4 blocks with breaks in between. The first PET acquisition block of 90 minutes duration (0 to 90 minutes) will be started together with the intravenous injection of 300±30 MBq (S)-(-)-[¹⁸F]fluspidine; the following acquisition blocks of 30 minutes duration each will be started at 2, 3, and 6 hours post-injection of the PET tracer. Each PET acquisition block will be acquired in list mode in order to allow variable subdivision into multiple time frames as detailed in the imaging manual.

The first dose of pridopidine will be high (90 mg) for subjects enrolled in the first dose cohort but may be changed to another dose based on PRIDE-HD study results. Subsequent doses (2.5, 5, 10, 22.5, 45, or 67.5 mg) will be determined on the basis of the RO results following PET session 2 and the time-activity profiles of (S)-(-)-[¹⁸F]fluspidine from previous cohort subjects. In addition, the timing of the PET sessions may also be revised. If any of the postdose PET investigations are compromised due to technical or logistic reasons, a repeat investigation may be considered, provided that the resulting cumulative radiation exposure by (S)-(-)-[¹⁸F]fluspidine for all PET sessions does not exceed the allowed overall study exposure (effective dose not exceeding 20 mSv), when using tracer administered activity of 300±30 MBq per PET session, and further respecting a washout of 7 days of pridopidine and its metabolites. PET session 2 will start at 2 hours postdose of pridopidine.

Up to 15 subjects may be evaluated in Part B to characterize the D2R binding of pridopidine. The cohort structure will also comprise up to 4 subjects. Each of the 2 PET sessions will consist of 4 subsets of acquisition blocks that will be acquired in list mode: 0 to 90 minutes, 120 to 150 minutes, 180 to 210 minutes, and 360 to 390 minutes post-injection of 200±20 MBq [¹⁸F]fallypride. Each PET acquisition block will be acquired in list mode in order to allow variable subdivision into multiple time frames, and will be according to the institutional standard as detailed further in the imaging manual. PET session 2 will start at approximately 2 hours postdose of pridopidine. The PET imaging protocol is essentially the same as for (S)-(-)-[¹⁸F]fluspidine. From the second block onwards, acquisition can commence within ±10 minutes of the nominal time, but the duration should still be 30 minutes for each of these blocks.

Brain MRI scans will be performed at screening to ensure subjects are qualified for the study but will also provide data to aid the analysis of PET data. Additional functional MRI scans (MR-AC, T1 MPRAGE 3D, ASL, 2D MRS, and rs-fMRI) will be performed in parallel with the PET imaging sessions to evaluate the relationship between brain activity and S1R or D2R occupancy by pridopidine. These scans will be further detailed in the imaging manual.

The dose of pridopidine in Part B will be determined based on the results obtained using (S)-(-)-[¹⁸F]fluspidine in Part A. The timing of the [¹⁸F]fallypride PET scan may also be revised. If any of the postdose PET investigations are compromised due to technical or logistic reasons, a repeat investigation may be considered, provided that the resulting cumulative [¹⁸F]fallypride dose for all PET sessions does not exceed the authorized overall study exposure (effective dose not exceeding 20 mSv), when using

tracer administered activity of 200 ± 20 MBq per PET session, and further respecting a washout of 7 days of pridopidine and its metabolites.

For the test-retest cohort (Part 0), fluspidine will be administered twice. The 2 tracer doses will be administered separately within a certain time frame, without pridopidine. The PET session 2 will take place at approximately a similar time of day (± 1 hour) as the baseline PET session 1, on another day (at least 24 hours ~ 10 half-lives ^{18}F apart)

Blood samples for determination of pridopidine and TV-45065 plasma concentrations and exploratory biomarkers will be collected during the timing of the PET examinations in visit 3.

Safety and tolerability (the number [%]) of healthy subjects and HD patients who failed to complete the study due to adverse events) will be assessed throughout the study by monitoring adverse events and by conducting clinical safety laboratory tests, ECG, physical examination, and vital sign assessments.

Study procedures and assessments with their time points are summarized in Table 1 of the study protocol.

2.2. Randomization and Blinding

This is a non-randomized, open-label study and there is no blinding.

2.3. Data Monitoring Committee

This study will not be overseen by a Data Monitoring Committee.

2.4. Sample Size and Power Considerations

This PET study is exploratory in nature; therefore, no formal hypothesis testing is planned. Thus, based on clinical and practical considerations, a sample size of up to approximately 38 subjects (up to 4 subjects per dose level) is considered adequate for this type of study and to attain the study objectives. Up to 45 subjects are planned to be enrolled in this study to ensure up to 38 evaluable subjects. Adaptive study design will allow increasing or reducing the study total sample size or each dose/time cohort as necessary. This sample size may include up to 4 patients with HD, which may be added to study engagement of pridopidine to the D2R and to explore the effects of neurodegeneration.

It is anticipated that 3 dose levels will be sufficient to characterize the exposure-response profile. However, additional cohorts may be studied.

2.5. Sequence of Planned Analyses

2.5.1. Planned Interim Analyses

There will be no formal interim analysis for this study. PET data will be analyzed after each cohort for selection of the next cohort dose.

2.5.2. Final Analyses and Reporting

All final, planned analyses for pharmacokinetic and safety measures identified in this SAP will be performed after the end of study as defined in the study protocol. This SAP and any corresponding amendments will be approved before database lock, in accordance with SOP GBP_RD_702 (SAP).

All analyses for pharmacodynamics (imaging data) will be detailed in the imaging manual prepared by [REDACTED]

[REDACTED]

[REDACTED]

3. ANALYSIS SETS

3.1. Enrolled Analysis Set

The enrolled analysis set will include all enrolled subjects, regardless of whether or not a subject took any study drug. A subject is considered enrolled according to the status reported in the database.

3.2. Safety Analysis Set

The safety analysis set will include all subjects who receive at least 1 dose of study drug (pridopidine or PET Tracer). In this analysis set, treatment will be assigned based on the treatment subjects actually received.

3.3. Pharmacokinetic Analysis Set

The pharmacokinetic analysis set will include those subjects in the safety analysis set who have sufficient data to calculate at least 1 evaluable pharmacokinetic parameter for pridopidine or its metabolites.

3.4. Pharmacodynamic Analysis Set

The pharmacodynamic analysis set will include those subjects in the safety analysis set who have evaluable imaging data before and after pridopidine administration. The decision about inclusion and exclusion of subjects in this analysis set will be done after Teva will receive final PD data.

4. GENERAL ISSUES FOR DATA ANALYSIS

4.1. General

Descriptive statistics for continuous variables include n, mean, standard deviation (SD), standard error (SE), median, minimum, and maximum. For continuous pharmacokinetic parameters (except t_{max}), the geometric mean will also be calculated. Descriptive statistics for categorical variables include subject counts and percentages, missing category will be displayed as appropriate.

For presentation the mean and median will be presented to 1 decimal greater than the original data, SD will be 2 greater than the original data and the minimum and maximum will have the same number of decimal places as the original data. The derived pharmacokinetic parameters will be summarized with a precision of 3 significant digits, while t_{max} will be presented with 2 decimals. The percentage coefficient of variation (CV) and frequency percentages will be presented with 1 decimal.

Tables will be presented by part and cohort, unless otherwise specified. Throughout the document cohort will mean the combination of dose level and population (healthy volunteers or patients with HD).

In case different dose levels are used within a cohort the cohort will be split by dose level. In case similar dose levels are used in different cohorts within the same population, these data may be pooled.

4.2. Specification of Baseline Values

Baseline for postdose evaluations is defined as the last observation recorded before the first study drug administration. The last observation can be an unscheduled / repeated measurement.

4.3. Handling Withdrawals and Missing Data

No imputation of missing data is planned, except for pharmacokinetic plasma concentration below the quantification limit (BQL) (see Section 9.3.1 and Section 9.3.2) and missing dates and times for AEs (see section 7.2).

4.4. Study Days and Visits

For by-visit (or by-time-point) summaries, if there are multiple assessments at a post baseline visit (or time point) then the scheduled assessment at that visit (or time point) will be used for the summary. For baseline and pre-baseline visits the last non-missing assessment at that visit (or time point) will be used for the summary (this includes scheduled and unscheduled assessments). For subjects who withdraw from the study, data at the early termination visit will be excluded from the by-visit summaries but will be included in the endpoint summaries.

An early termination visit is defined as the follow-up visit for a subject that did not complete the study.

Unscheduled measurements will be listed in the individual data listings.

Study days will be numbered relative to the first day of study drug administration in each visit (ie, visit 2 and visit 3). The start of treatment (day 1) is defined as the date on which a subject takes the first dose of study drug, as recorded on the CRF. Days will be numbered relative to treatment start (ie, ..., -2, -1, 1, 2, ...; with day 1 being the first day of study drug administration and day -1 being the day before the first day of study drug administration).

5. STUDY POPULATION

5.1. General

The enrolled analysis set will be used for all study population summaries unless otherwise specified. Summaries will be presented by part and cohort, unless otherwise specified.

5.2. Subject Disposition

Data from subjects screened, subjects screened but not enrolled (and reason not enrolled), subjects who are enrolled, subjects enrolled but not treated (and reason), subjects in the safety and pharmacokinetic analysis sets, subjects who complete the study, and subjects who withdraw from the study will be summarized using descriptive statistics. Data from subjects who withdraw from the study will also be summarized by reason for withdrawal using descriptive statistics. The data will also be presented in a listing.

5.3. Demographics and Baseline Characteristics

Subject demographic and baseline characteristics, including medical history, and prior medications will be summarized using descriptive statistics by part and cohort. The results of the C-SSRS at screening will be listed.

5.4. Medical History

All medical history will be coded using the Medical Dictionary for Regulatory Activities (MedDRA). The incidence of medical history abnormalities will be summarized using descriptive statistics by system organ class (SOC) and preferred term. Subjects are counted only once in each preferred term and SOC category.

5.5. Prior Therapy and Medication

Medications administered prior to any study drug administration will be recorded as prior medications and medications administered following the first dose and throughout the study will be recorded as concomitant medication. Any prior therapy, medication, or procedure a subject has had within 28 days before study drug administration will be recorded on the CRF. Trade name or INN, indication, dosage, and dosing start and stop times will be recorded. The sponsor will encode all therapy and medication according to the World Health Organization drug dictionary (WHODD).

5.6. Study Protocol Violations

Data from subjects with any protocol violations (as recorded in the protocol violation CRF) during the study will be summarized overall and for each category using subject counts and percentages.

6. MULTIPLE COMPARISONS AND MULTIPLICITY

No adjustments will be made for the preplanned multiple comparisons/endpoints.

7. SAFETY ANALYSIS

7.1. General

The safety analysis set will be used for all safety analyses. Summaries will be presented by part and cohort, unless otherwise stated.

7.2. Adverse Events

All adverse events will be coded using MedDRA.

Adverse events present before the first administration of study drug (PET tracer) will not be included in the summaries.

The incidence of adverse events will be summarized using descriptive statistics by SOC and preferred term. Each subject will be counted only once in each preferred term or SOC category for the analyses of safety. Summaries will be presented for all adverse events (overall and by severity), adverse events determined by the investigator to be related to study treatment (ie, reasonable possibility) (overall and by severity), serious adverse events, and adverse events causing withdrawal from the study. For the summaries by severity, subjects are counted at the highest severity. Summaries will be presented by part, cohort and total by population for all subjects.

All adverse events (including events started before the first administration of study drug) recorded on the CRF will be listed. Subject listings of serious adverse events and adverse events leading to withdrawal will also be presented.

The following missing data will be imputed as defined (for calculations only, will not be presented):

- Missing AE start and / or end times for the calculation of onset and duration will be assumed to be at 00:01 for a start time and 23:59 for end times
- Missing AE severity or relationship will be assumed to be severe or related, respectively
- Missing AE start times for the determination of treatment emergence will be assumed to occur after treatment unless partial date documents the AE as happening prior to treatment
- Missing AE start times for the determination of treatment assignment will be assumed to occur after treatment on the recorded date
- Missing AE start date will be assumed to be after treatment for deaths and SAEs.

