^c Events that occurred prior to the signing of the informed consent form will be recorded in the medical history.

^d Medications administered prior to any study drug administration will be recorded as prior medications.

^e Corticoid plasma levels, to be taken directly prior to tracer dosing (DHEA, progesterone, testosterone, cortisol, where feasible also androstanolone, allopregnanolone, pregnenolone).

^f Virology testing will include: human immunodeficiency virus (HIV-1, HIV 2), HBsAg, and/or hepatitis C.

^g Height, weight, and body mass index will be measured only at screening. Complete physical examination on screening and follow up/early termination visits only. On other occasions, abbreviated/symptom- oriented physical examination will be conducted.

^h Part 0 and Part A subjects only.

ⁱ The 12-lead ECG is to be performed before pridopidine administration; immediately before administration of the tracer (approximately 90 minutes after pridopidine administration), and at the end of the first PET scan (approximately 3.5 hours after pridopidine administration). When ECG collection coincides with a pharmacokinetic sample, ECG will be collected before the pharmacokinetic sample.

^j Vital signs (pulse, respiratory rate, body temperature, and systolic and diastolic BP) will be measured with the subject seated or supine immediately prior to administration of pridopidine, and prior to and immediately after each PET scan. BP will be measured in the same arm throughout the study, whenever possible. When vital signs collection coincides with PK sample, vital signs will be collected before the PK sample.

^k Except for test-retest cohort (Part 0).

^l [¹⁸F]fluspidine for Parts A and 0, [¹⁸F]fallypride administration for Part B.

^m This should be performed as the final procedure of the screening visit, after all other eligibility criteria have been fulfilled.

ⁿ For the test-retest cohort, fluspidine will be administered twice. The 2 tracer doses will be administered separately within a certain time frame, without pridopidine. The PET session 2 will take place at approximately a similar time of day (± 1 hour) as the baseline PET session 1, on another day (at least 24 hours ~ 10 half-lives ^{18}F apart).

^o In an effort to facilitate easier PET procedure for HD patients, after the first 90-minute PET acquisition block, the subsequent 30-minute PET acquisition blocks are made optional per Investigator's judgement (refer to study Imaging Manual for details).

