9.10.2. Safety Analysis

All adverse events will be coded using the Medical Dictionary for Regulatory Activities (MedDRA). Each subject will be counted only once in each preferred term or SOC category for the analyses of safety. Summaries will be presented for all adverse events (overall and by severity), adverse events determined by the investigator to be related to study treatment (ie, reasonable possibility; see Section 7.1.4) (defined as related or with missing relationship) (overall and by severity), serious adverse events, and adverse events causing withdrawal from the study. Summaries will be presented by treatment group and for all subjects. Subject listings of serious adverse events and adverse events leading to withdrawal will be presented.

Changes in laboratory and vital signs measurement data will be summarized descriptively. All values will be compared with predefined criteria to identify potentially clinically significant values or changes, and such values will be listed.

The use of concomitant medications will be summarized by therapeutic class using descriptive statistics. Concomitant medications will include all medications taken while the subject is treated with study drug.

For continuous variables, descriptive statistics (n, mean, SD, median, minimum, and maximum) will be provided for actual values and changes from baseline to each time point. For categorical variables, subject counts and percentages will be provided. Descriptive summaries of serious adverse events, subject withdrawals due to adverse events, and potentially clinically significant abnormal values (clinical laboratory or vital signs) based on predefined criteria will be provided as well.

If any subject dies during the study, a listing of deaths will be provided and all relevant information will be discussed in the subject narrative included in the CSR.

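### The healthy-subject adverse-event total in SAP 7.2 is not an incidence among pridopidine-exposed subjects: as written it most naturally includes tracer-only subjects and events before pridopidine

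*SAP*

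**What the plan says.** - **Who is in the safety set.** SAP 3.2 includes "all subjects who receive at least 1 dose of study drug (pridopidine or PET Tracer". SAP 7.1 adds: "The safety analysis set will be used for all safety analyses". Protocol 9.2.2 does not mention tracers in its definition. Where the two documents differ, the SAP's Introduction gives the SAP precedence.
- **What Part 0 receives.** SAP 2.1 says of the test-retest cohort: "The 2 tracer doses will be administered separately within a certain time frame, without pridopidine". The note on pridopidine administration under Table 1 in Protocol 3.14 agrees: "Except for test-retest cohort (Part 0". Both documents describe Part 0 subjects as healthy.
- **What a population is.** SAP 4.1: "cohort will mean the combination of dose level and population (healthy volunteers or patients with HD". There are two populations, and Part 0 belongs to the healthy one.
- **How adverse events are totalled.** SAP 7.2: "Summaries will be presented by part, cohort and total by population for all subjects". Protocol 9.10.2: "Summaries will be presented by treatment group and for all subjects".
- **When counting starts.** SAP 7.2 leaves out only events already present before the first study drug, which it identifies as the tracer. In Parts A and B that is visit 2; pridopidine follows at visit 3.
- **What the tables serve.** A secondary objective in SAP 1.1.1 is the safety of pridopidine in healthy subjects and HD patients.

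No sentence limits any adverse-event total to subjects who received pridopidine.

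**The concern.** Dose cohorts have up to 4 subjects, so a single cohort column says little about how often an event occurs. The population total is the column that pools across cohorts, and it is the obvious one to consult for the safety objective. As written, neither part of that fraction is tied to pridopidine:

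- The denominator takes in Part 0. It also takes in any Part A or B subject who had the visit 2 tracer and left before dosing.
- The numerator takes in events between the visit 2 tracer and the pridopidine dose.

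Someone who reads the total as the adverse-event rate on pridopidine would be reading a mixture of exposed subjects, unexposed subjects and unexposed time.

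**Working it through.** **The plan's own figure.** The Protocol synopsis splits the evaluable subjects as 20 (Part A) + 15 (Part B) + 3 (Part 0) = 38, which matches the stated 38. SAP 2.1 also gives 3 for Part 0, but Protocol 3.1 allows up to 6, and 20 + 15 + 6 = 41. Both sizes are carried below.

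**Inputs.** Dosed subjects: 20 + 15 = 35, assuming everyone in Parts A and B is dosed. Up to 4 of the sample may be HD patients (SAP 2.4); if they are among the 35, then 31 dosed subjects are healthy. Part 0 size n0 is 3 or 6. The documents give no adverse-event rates, so every rate below is an assumption.

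**Step 1: events caused by pridopidine.** Part 0 can have none, so the total multiplies their incidence by n_dosed / (n_dosed + n0).

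| Part 0 | HD among the 35 | Healthy dosed | Healthy total | Factor | An assumed 20% reads as |
|---|---|---|---|---|---|
| 3 | 0 | 35 | 38 | 0.921 | 18.4% |
| 3 | 4 | 31 | 34 | 0.912 | 18.2% |
| 6 | 0 | 35 | 41 | 0.854 | 17.1% |
| 6 | 4 | 31 | 37 | 0.838 | 16.8% |

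Each Part A or B subject who leaves between the visit 2 tracer and pridopidine adds one more to the denominator. The documents give no expected number, so none is included.

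**Step 2: all-cause events, denominator effect only.** Pooled rate = (n_dosed × p_dosed + n0 × p_0) / (n_dosed + n0). With p_dosed = 30% and no HD patients:

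| Part 0 rate p_0 | n0 = 3 | n0 = 6 |
|---|---|---|
| 0 | 27.6% | 25.6% |
| 15% (half) | 28.8% | 27.8% |
| 30% (equal) | 30.0% | 30.0% |
| 45% (1.5 times) | 31.2% | 32.2% |

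The sign depends entirely on p_0.

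**Step 3: adding events before pridopidine.** Let v be the chance that one tracer session alone produces a counted event, taken as independent of pridopidine. Keep the post-pridopidine rate at 30%. A dosed subject is counted with probability 1 − 0.70(1 − v). A Part 0 subject, with two sessions, is counted with probability 1 − (1 − v)². Pooled rate = [35 × (1 − 0.70(1 − v)) + n0 × (1 − (1 − v)²)] / (35 + n0).

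| v | n0 = 3 | n0 = 6 |
|---|---|---|
| 0 | 27.6% | 25.6% |
| 5% | 31.6% | 30.0% |
| 10% | 35.6% | 34.4% |

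The pooled rate equals the assumed 30% at v = 3.0% (n0 = 3) or v = 5.0% (n0 = 6), and exceeds it above that.

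**The case against.** **The total may be meant within each part.** Part and cohort is the default layout in SAP 7.1, so a population total inside each part is a possible reading, and Part 0 would then not be pooled. This stands as a possibility. The pooled reading is more natural, because SAP 7.2 goes beyond that default and extends the total to all subjects, as Protocol 9.10.2 does. Even within part, the Part A and B totals would still hold subjects who left after the tracer, and events from visit 2.

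**Readers can take Part 0 out themselves.** Part 0 has its own columns and every event is listed, so this stands, and it confines the pooling to the total column. It does not help with a Part A or B subject who was never dosed: SAP 4.1 builds cohorts from dose level, so that subject has no defined cohort column. Nor does it separate visit 2 events, because the same counting rule applies in the cohort columns.

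**The plan does not call this a pridopidine rate.** The study is descriptive, with no control arm and no hypothesis test, and a dosed-only total would still pool different doses. All of this stands and limits the weight of the point.

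**The table of related events might isolate pridopidine.** It does not. It uses relation to study treatment, while SAP 3.2 and Protocol 7.1.8 both count tracers as study drug, and SAP 7.2 treats a missing relationship as related.

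**A stronger reading is tempting.** A reader might infer that the total understates the adverse-event rate and leans towards showing no effect. The documents do not support that for all-cause events. They give no Part 0 rate. Part 0 subjects have two tracer sessions with arterial cannulation, and visit 2 events push the dosed subjects' count up. Steps 2 and 3 show that the net error can take either sign.

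**Conclusion.** On the most natural reading, the healthy-subject total in SAP 7.2 is not an incidence among subjects exposed to pridopidine, and so does not match the stated safety objective.

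- **Pridopidine-caused events:** the total lowers their incidence by a factor of 0.921 with 3 Part 0 subjects, or 0.854 with 6 (0.912 and 0.838 if 4 of the 35 are HD patients). This assumes 35 dosed subjects and nobody leaving between the visit 2 tracer and pridopidine.
- **All-cause events:** neither the size nor the direction of the net error can be derived from the documents. The same factors would apply only if Part 0 had no counted events of any kind and no event before pridopidine were counted in Parts A and B.

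The composition of the total is well supported, subject to the within-part reading. The point is worth fixing but limited, since it concerns descriptive tables whose part and cohort components are shown separately.

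**What to change.** In SAP 7.2, replace the population total with two defined totals: all pridopidine-dosed healthy subjects and all pridopidine-dosed HD patients. Count only adverse events with onset at or after the pridopidine dose.

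Show Part 0, any other tracer-only subjects, and events between the visit 2 tracer and pridopidine in a separate tracer-only column, outside both totals. If an additional total within each part is wanted, say so. Reconcile the Part 0 size of 3 in SAP 2.1 with the up to 6 in Protocol 3.1.

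The cost is one or two extra table columns and a flag that assigns each event to the period before or after pridopidine. Onset dates and times are already recorded (Protocol 7.1.2), and SAP 7.2 already has rules for missing start times that the flag can use. No new data are needed.
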